4.4.3 Handling of Withdrawals

If a participant wishes to withdraw from the study and all assessments, his/her intention will be honored. For withdrawn participants, data will be retained and used at the discretion of the investigator.

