4.4 Treatment Assignment Procedures

4.4.1 Randomization Procedures

Following baseline assessment, participants will be randomized to complete either the combined treatment (active tDCS plus cognitive training) or cognitive training alone (sham tDCS). Participants and clinical assessors will be blinded to condition; at the post-treatment assessment visit, participants and the assessor will guess group assignment to evaluate how well the blind was maintained.

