4.4.2 Reasons for Withdrawal

During the pre-screening process, participants who are found to be non-eligible, before formal signing of a consent form, will be considered *not enrolled*, and all data related to that participant will be destroyed. Participants who consent, and are found not eligible during the assessment and screening will be considered *screen failures*, and all research and identifying data will be destroyed, except for the consent form and limited information to document the screen failure (age, gender, diagnosis, specific reason for exclusion). Participants who leave the study after signing the informed consent, and after being deemed eligible/enrolled/randomized, will be considered *withdrawn*. Participants may withdraw from the study at any time and for any reason. Participants may be withdrawn by the investigator when continued participation would present an unacceptable risk to the participant. This would include, but is not limited to, significant adverse events related to the device, (e. g., intolerable discomfort), or participants who experience severe symptom worsening, including suicidal thoughts or behaviors, which require hospitalization.

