5.2.4 Early Termination Assessments

If early termination occurs and, if the participant is willing and able, all of the outcomes and safety assessments noted above for the final experimental visit will be performed.

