5.5 Assessments

Participants will complete assessments at three time points: baseline (pre-treatment), post-treatment, and follow-up.

Assessment schedule and administration time requirements.

	Baseline	Post-treatment	Follow-up	Administration time (mins)
Clinical measures				
MINI diagnostic interview	x			60
HAM-D, YMRS, PANSS	x	x	x	15-30
C-SSRS	x			5
Neuropsychological measures				
WRAT reading	x			5
MCCB (Trails A*; letter-number span; spatial span)	x	x	x	30
Trails B*	x	x	x	5
Functional measures				
SLOF	x	x	x	10
Total estimated time	≤ 2.5 hours	≤ 1.5 hours	≤ 1.5 hours	

*Trails A and B will be administered as non-working memory neurocognitive comparison measures

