6.2 Event Windows, Missed Assessments/Sessions and Protocol Deviation Reporting

For the post-treatment and follow-up assessments, a window of \pm 10 days will be permitted (not including weekends). Any safety-related assessments (HAM-D, YMRS, PANSS, C-SSRS) or primary outcome measure (MCCB working memory) which are missed or obtained outside the window will be reported to the IRB as a protocol deviation. However, for the other assessments, missing or late assessments will not be reported as protocol deviations unless they constitute > 10% of the total assessments. In order to accommodate inevitable scheduling conflicts, holidays, etc., participants will be allowed to complete the 10 tDCS sessions within 4 weeks. Participants who do not complete all 10 tDCS sessions or all 10 hours of cognitive training will be retained in the study and their outcome data will be compared to those participants who completed the full course of treatment. These allowances should affect neither the scientific integrity nor the safety monitoring provisions of the protocol.

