8.0 Statistical Analysis

8.1 Data Analysis

Specific Aim 1: Feasibility will be evaluated through participant retention, and will be calculated as the percentage of enrolled participants who complete the combined intervention. Acceptability will be evaluated by participant-rated satisfaction with the intervention, as rated on a 1-10 scale (where 1 is low satisfaction and 10 is high) collected at study completion.

Specific Aim 2: Mixed-factorial ANOVA will be used to examine between-group (Group A: active tDCS, versus Group B: sham tDCS) and within-group (time) effects on the main outcome measures: MCCB letter-number span score and MCCB spatial span score. Mean performance for each group at each time point will be plotted and examined.

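### Aim 2: section 4.4.3 leaves use of withdrawn randomised participants' data to the investigator and 8.1 names no analysis set, so selection after results are seen is permitted, though not shown

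*Combined protocol and SAP*

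**What the plan says.** The rule is in 4.4.3: "For withdrawn participants, data will be retained and used at the discretion of the investigator". Section 4.4.2 defines whom it covers: "Participants who leave the study after signing the informed consent, and after being deemed eligible/enrolled/randomized, will be considered" withdrawn. Departure is not always the participant's choice: "Participants may be withdrawn by the investigator when continued participation would present an unacceptable risk to the participant".

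Withdrawn people can have outcome data. On early termination, 5.2.4 provides that "if the participant is willing and able, all of the outcomes and safety assessments noted above for the final experimental visit will be performed".

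On blinding, 4.4.1 says "Participants and clinical assessors will be blinded to condition". It does not mention the investigator.

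The Aim 2 analysis in 8.1 is one method applied to two main measures, letter-number span and spatial span: "Mixed-factorial ANOVA will be used to examine between-group" and time effects. It names no analysis set, lists no time points and gives no rule for missing values. Section 5.5 sets the visits: "Participants will complete assessments at three time points: baseline (pre-treatment), post-treatment, and follow-up".

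Section 6.2 deals with people who fall short on sessions or training hours. They "will be retained in the study and their outcome data will be compared to those participants who completed the full course of treatment". Section 6.1.2 only points back to 4.4.2-4.4.4.

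The Protocol Summary counts Aim 2 as 30 completers. Section 1.0 counts 30 enrolled, and 3.1 and the 3.4 schematic put 15 in each arm.

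**The concern.** Aim 2 tests whether active tDCS plus training is superior to sham plus training. That comparison keeps its nominal error rate only if the people in it are fixed without knowledge of the results by arm. Under 4.4.3 the investigator, who may withdraw a participant, also decides whether that participant's data count, and may do so at any time. A reader of the report could not tell whether the analysed group was fixed beforehand.

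The intended group cannot be inferred from the sample size either. If 30 means completers, the withdrawn look like extras outside the planned analysis. If 30 means randomised, leaving them out departs from the plan. The trial is a pilot, but the Protocol Summary says its result is to support further work in larger samples.

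**Working it through.** **Step 1: which provisions limit the discretion.**

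- 6.2 keeps people who miss sessions or training hours, so the discretion reaches only those who leave the study. It sets partial against full completers and does not say who enters active versus sham.
- 5.2.4 supplies data for some who leave, but no section says which time point such a value fills.
- 8.1 gives Aim 1 retention a denominator (those enrolled). Aim 2 has no counterpart.
- A classical ANOVA on all three time points drops anyone who leaves before post-treatment, whatever the investigator decides. The choice then matters only for people who leave after post-treatment and whose early-termination assessment could stand as follow-up.
- With baseline and post-treatment only, the choice also reaches people who withdraw in the no-contact month, and early leavers with an early-termination assessment. Section 8.1 does not say which version applies.

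**Step 2: what the choice can do to type I error.** The documents state no alpha, power, effect size, SD or dropout rate, so there is no figure to reproduce. Every input below except 15 per arm is assumed: alpha 5%, no true effect, normal data, withdrawal at random, one outcome.

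*All in or all out.* The test is the ANOVA arm-by-time F test with (T-1) and (T-1)(N-2) degrees of freedom. For T = 3 and N = 30 these are 2 and 56; with 6 people removed, 2 and 44. The error rate of the better of two analyses is P(min(p for completers, p for completers plus withdrawn) < 0.05). Between-visit correlation is 0.6, with 40,000 simulated trials per row, so the simulation error near 5% is sqrt(0.05 × 0.95 / 40,000) = 0.1 points.

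| Withdrawn of 30 | With usable data | Completers, fixed (3 time points) | Plus withdrawn, fixed (3 time points) | Better of the two, 3 time points | Better of the two, 2 time points |
|---|---|---|---|---|---|
| 3 | 1 | 4.9% | 5.0% | 5.9% | 5.9% |
| 3 | 3 | 4.9% | 4.9% | 6.5% | 6.6% |
| 6 | 2 | 5.1% | 5.1% | 6.5% | 6.4% |
| 6 | 6 | 5.1% | 5.1% | 7.4% | 7.2% |
| 9 | 3 | 5.1% | 5.1% | 7.0% | 6.8% |
| 9 | 9 | 5.1% | 5.2% | 8.1% | 7.8% |

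With 6 of 6 and three time points, a correlation of 0.4 or 0.8 gives 7.3% in each case. With no usable data there is nothing to choose and the rate stays at 5%.

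*Person by person.* The wording of 4.4.3 allows this too. With w withdrawn per arm, all with data, there are 2^(2w) possible analyses: 4, 16 and 64 for w = 1, 2, 3. The test is t = (mean A - mean B) / sqrt(s²(1/nA + 1/nB)) on change from baseline to post-treatment, which equals the arm-by-time test at two time points. There were 20,000 simulated trials per case.

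| Withdrawn per arm | 15 randomised per arm: all in or out | Person by person | 15 completers per arm plus withdrawn: all in or out | Person by person |
|---|---|---|---|---|
| 1 | 6.2% | 6.9% | 6.2% | 6.8% |
| 2 | 6.8% | 9.4% | 6.7% | 9.2% |
| 3 | 7.2% | 12.7% | 6.9% | 12.0% |

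The size is therefore much the same under either reading of the 30.

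**Step 3: does the replacement model hold its level?** A REML repeated-measures model with unstructured covariance was fitted to all available data with 0, 3, 6 and 9 of 30 withdrawn. One third of the withdrawn had baseline only, one third baseline and post-treatment, and one third all three values. There were 6,000 trials per case, with simulation error about 0.3 points.

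- One contrast: uncorrected 6.3, 6.4, 5.8, 6.1%; Kenward-Roger 5.2, 5.3, 4.8, 5.1%.
- Two-df interaction: uncorrected 6.9, 8.3, 8.1, 8.3%; Kenward-Roger 5.0, 5.4, 5.5, 5.2%.

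At this sample size the small-sample correction is needed.

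**The case against.** The best defence is that 4.4.3 may be mainly a retention clause, next to the rules in 4.4.2 on destroying screening data, and that Aim 2 collects pilot data with no declared alpha. Both points lower the stakes. They do not change the fact that the sentence governs use as well as retention, or that 8.1 still compares the arms.

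A second objection is that the upper figures are remote. For three time points they need every withdrawn person to have all three values. That means leaving after post-treatment with an assessment that can serve as follow-up, and 5.2.4 sits under the treatment visits, so its use in the no-contact month is itself an inference. This stands: the one-third rows and the 5% floor are as plausible as the top rows.

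A third is that a fixed set alone restores the error rate, so a new model goes beyond the defect. That is correct for type I error. But a classical ANOVA needing every time point would discard people whom the fixed set is meant to keep, so the model is needed to carry the set out.

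Readers might infer more than the text supports:

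- *The investigator is unblinded.* Section 4.4.1 is silent on this, and silence is not evidence.
- *More people will leave the active arm, so the bias has a known direction.* Sections 4.4.2 and 5.2.3 tie withdrawal to side effects and symptom worsening, which makes arm-related loss possible. Section 11.3.3 reports similar sensation frequencies for real and sham tDCS, but as percentages of studies, which says little about withdrawal by arm.

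**Conclusion.** The point holds as a gap in the Aim 2 rules. The plan permits the analysed group to be chosen after results are seen, and no other section closes this off. It does not show that selection took place or was planned, and it does not establish the direction of any bias. Nor are partial completers at risk, since 6.2 keeps them, and Aim 1 retention is untouched because it is counted on those enrolled.

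The size is about 6-8% instead of 5% for an all-in or all-out choice with 3-9 of 30 withdrawn. It is about 7-13% for deliberate person-by-person choice with 1-3 withdrawn per arm, all with data, and 5% if nobody withdrawn has usable data. These figures rest on the assumptions listed in the working. They cover one outcome, whereas 8.1 names two, and they do not include bias from withdrawal related to outcome. This is a cheap improvement worth making, not a fault that defeats the trial.

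**What to change.** 1. For Aim 2, replace the discretion sentence in 4.4.3 with: *All randomised Aim 2 participants are analysed in the arm assigned, using all outcome data collected, except data the participant does not permit to be used; any other exclusion is decided and documented blind to arm before outcomes are examined by arm.*
2. State in 8.1 that this is the primary set for Aim 2, and reconcile the 30 completers of the Protocol Summary with the 30 enrolled in 1.0 and the 15 randomised per arm in 3.1.
3. In 8.1, replace the classical ANOVA with a likelihood-based repeated-measures model (arm, time, arm by time) with a Kenward-Roger correction, so that people with a missing time point are not dropped.
4. Before unblinding, fix which time point an early-termination assessment represents. Add a sensitivity analysis leaving those values out, because a value taken after a few sessions may not represent a completed course.

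Aim 1 and the 6.2 comparison need not change. The cost is new wording in 4.4.3, a different model in 8.1 and slightly more analysis work, with no added visits or participants. The effect in all randomised participants may be smaller than among completers. If the sponsor prefers to keep the ANOVA, items 1 and 2 still remove the discretion.

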4.4.4 Termination of Study

This study may be prematurely terminated if, in the opinion of the investigator or the sponsor, there is sufficient reasonable cause. Written notification, documenting the reason for study termination, will be provided to the investigator or sponsor by the terminating party. Circumstances that may warrant termination include, but are not limited to: determination of unexpected, significant, or unacceptable risk to participants; insufficient adherence to protocol requirements; data that are not sufficiently complete and/or evaluable. If the study is prematurely terminated or suspended, the PI will promptly inform the IRB and will provide the reason for the termination or suspension.

4.5 Pre-Screening

Potential participants will be screened informally, usually over the telephone, possibly face-to-face (see pre-screening form) in order to make a preliminary assessment of their eligibility. Patients who appear eligible and express interest in participating will be scheduled for a screening/assessment visit.

5.0 Study Schedule

5.1 Screening and Initial Assessment Visit

5.1.1 Informed Consent

The session will begin by having the participant provide written informed consent. Informed consent is a process that is initiated prior to the individual's agreeing to participate in the study and continues throughout the individual's study participation. Extensive discussion of risks and possible benefits of these treatments will be provided to the participants and any family members or others the participant would like to include in the process. Consent forms (written in non-technical language) describing in detail the study interventions/products, study procedures, and risks will be given to the participant and written documentation of informed consent is required prior to starting the intervention. Consent forms will be IRB-approved and the participant will be asked to read and review the document. Upon reviewing the document, the investigator (or her designee) will explain the research study to the participant and answer any questions that may arise. The participant will sign the informed consent document prior to any procedures being done specifically for the study. Participants will have the opportunity to discuss the study with their surrogates or think about it prior to agreeing to participate.

Participants may withdraw consent at any time throughout the course of the trial. A copy of the informed consent document will be given to participants for their records. The rights and welfare of the participants will be protected by emphasizing to them that the quality of their medical care will not be adversely affected if they decline to participate in this study.

5.1.2 Initial Assessments

This session will continue with completion of a brief demographic questionnaire and clinical measures to confirm eligibility and characterize current symptoms. These include:

1. Mini-International Neuropsychiatric Interview (MINI), a short structured diagnostic interview for DSM-IV and ICD-10 psychiatric disorders
2. Hamilton Depression Rating Scale (HAM-D)
3. Young Mania Rating Scale (YMRS)
4. Positive and Negative Syndrome Scale (PANSS)
5. Columbia Suicide Severity Rating Scale (C-SSRS)

Note. To allow for maximal appropriate distancing owing to the ongoing COVID-19 pandemic, these interview-based clinical measures may be completed virtually while the participant is physically in the building and the clinician is in a remote location, via a secure and approved telehealth platform (Zoom for Health). Because the participant will be in the clinic with another study staff member (who will be administering the informed consent and the portion of the assessment that requires manipulation of materials), there are no anticipated changes to safety or risk-assessment protocols. Any safety concerns will be immediately communicated between the study clinician and research assistant, and appropriate action will be taken (see section 5.5.1).

Neuropsychological and functional measures will also be administered to characterize current neurocognitive functioning. These include:

1. Wide Range Achievement Test, reading subtest (WRAT-4)
2. MCCB: Trails A, letter-number span, spatial span
3. Trails B
4. Specific Levels of Functioning (SLOF) clinician-rated questionnaire

This screening and initial assessment visit is expected to last up to 2.5 hours.

5.2 tDCS Treatment visits

5.2.1 Overview

tDCS traditionally uses two electrodes (an anode and a cathode) that are placed according to the international 10-20 system (or the extended 10-20 system), allowing for easy replication both within and across studies. The neurons underlying the anode become depolarized ("excited") whereas those underlying the cathode become hyperpolarized ("inhibited"). A study team member will be present in the room with the participant during the stimulation session. tDCS is administered while the participant sits in a chair. Following placement of the electrodes, either active or sham tDCS will commence: in both conditions, a brief ramp up period will occur first in which the electrical current is gradually increased. In the active condition, the current will reach 2mA and will be sustained at that level for 20 minutes, then a ramp down period will take place during which the current is gradually removed. The sham condition mirrors the ramp up and ramp down of active stimulation but does not otherwise deliver a current. The proposed montage includes anodal (excitatory) stimulation over the left dorsolateral prefrontal cortex, and cathodal (inhibitory) stimulation over right dorsolateral prefrontal cortex. The exact duration, frequency and amount of stimulation may vary from these procedures based on feedback from participants (but will not exceed 2 mA or 20 minutes), so the parameters will always fall within the safety guidelines. For example, if a participant reports discomfort, stimulation will be paused and additional saline/gel will be added to improve the contact (i.e., reduce resistance), or the current will be incrementally reduced to a tolerable level. The participant will concurrently complete BrainHQ working memory exercises during and immediately after the stimulation session, for approximately 60 minutes total. Treatment will occur in a designated room on the second floor of the Rachel Upjohn Building, department of Psychiatry.

5.2.2 Treatment Device

A Soterix Clinical Trial (CT) stimulator will be used. The unit is powered by standard 9v batteries and has a number of built-in safety features that limit the maximum possible current to the programmed parameters. The unit includes a switch to select active or sham stimulation. This unit is considered an investigational device by the FDA. Based on the scientific literature available to date, this device is believed to be of non-significant risk (NSR).

5.2.3 Stopping Rules

In the event that a participant reports discomfort during the tDCS procedure, stimulation will be paused and additional saline/gel will be added to improve the contact, or the current will be incrementally reduced. The session will be discontinued if the patient reports continued discomfort. Immediately after each stimulation session ends, participants will complete a tDCS side effects questionnaire. A study team member will review the responses and will immediately consult the PI if a participant reports a moderate-severe rating for any of the side effects. Those participants, if any, will be given the option of withdrawing from the study. The PI will also withdraw participants if the nature of the side effect is unusual (i.e., not listed as a common side effect) or concerning (e.g., significant acute mood change). Clinically trained study staff will monitor participants closely for mood changes and/or any emergence of suicidal ideation throughout the duration of participation. Participants will be withdrawn in the event of significant symptomatic worsening, including:

1. Current mania: YMRS change of ≥ 7 points at mid-point assessment or clinical observation indicating current mania
2. Worsening of depressive symptoms: 25% increase (i.e., greater severity) in HAM-D total score at mid-point assessment
3. Worsening of psychosis: 25% increase (i.e., greater severity) in PANSS positive total score at mid-point assessment
4. Suicide risk evaluated by a clinician to be high and imminent (e.g., current suicide plan and intent)

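### Side-effect and symptom stops under 5.2.3 lead out of the study while 6.2 retains everyone with incomplete treatment, and no text keeps withdrawn participants on the scheduled span tests

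*Combined protocol and SAP*

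**What the plan says.** Section 5.2.3 (Stopping Rules) has several levels of consequence.

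- Discomfort that persists after the procedure has been adjusted: "The session will be discontinued if the patient reports continued discomfort". Nothing further follows from that sentence.
- A moderate-severe rating for any side effect: "Those participants, if any, will be given the option of withdrawing from the study".
- Unusual or concerning side effects: "The PI will also withdraw participants if the nature of the side effect is unusual" or concerning.
- Symptoms: "Participants will be withdrawn in the event of significant symptomatic worsening, including" four listed grounds. Three of these use scores on the YMRS, HAM-D and PANSS, for example "25% increase (i.e., greater severity) in HAM-D total score at mid-point assessment". The mania ground can also be met by clinical observation, and the fourth ground is high and imminent suicide risk.

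Section 4.4.2 defines the resulting status: "Participants who leave the study after signing the informed consent, and after being deemed eligible/enrolled/randomized, will be considered" withdrawn. It has no category for someone who stops stimulation but stays in follow-up.

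Section 5.2.4 provides for an assessment at early termination, conditional on the participant being willing and able: "all of the outcomes and safety assessments noted above for the final experimental visit will be performed".

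Section 6.2 says: "Participants who do not complete all 10 tDCS sessions or all 10 hours of cognitive training will be retained in the study", and that their outcomes will be compared with those of participants who completed treatment. It makes no exception for stops under 5.2.3.

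**The concern.** Someone withdrawn under 5.2.3 before session 10 has also not completed all 10 sessions. By 5.2.3 and 4.4.2 that person has left the study; by 6.2 that person is still in it. No sentence says which rule governs. The answer decides whether the MCCB letter-number span and spatial span are measured at the post-treatment and follow-up visits.

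The affected participants are not a random subset. They are selected on tolerability or on symptoms, either of which may depend on the assigned arm and on cognitive performance. Section 8.1 specifies a mixed-factorial ANOVA over time and names neither an analysis set nor a way to handle missing scores. If withdrawn participants have no scheduled scores, the Aim 2 comparison may end up describing those who tolerated treatment rather than those who were randomised.

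**Working it through.** The plan gives no drop-out rate, SD, effect size or power calculation, so there is no figure of its own to reproduce. The check has three parts.

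**1. Which Aim 2 tests each ground puts at risk.** The Aim 2 schematic in 3.4 and the schedule in 5.5 give three assessments: baseline, post-treatment (end of Week 4) and follow-up (Week 8). A mid-point assessment appears only in the Aim 1 schematic.

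| Ground | Consequence as written | Aim 2 span tests at risk |
|---|---|---|
| Continued discomfort (5.2.3) | That session ends | None from this rule alone; 4.4.2 separately allows the investigator to withdraw for intolerable discomfort |
| Moderate-severe side-effect rating | Option to leave the study | Post-treatment and follow-up, if the option is taken |
| Unusual or concerning side effect | Withdrawn | Post-treatment and follow-up |
| Mania on clinical observation; high suicide risk | Withdrawn | Post-treatment and follow-up, if before the post-treatment visit |
| Scored YMRS, HAM-D or PANSS change | Withdrawn, at a visit Aim 2 does not have | If the end-of-Week-4 visit is meant, follow-up only: the span tests are due at that same visit and treatment is over |

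The scored exits need not be rare. Entry requires a HAM-D below 17 (4.2), and a 25% rise is 1 point from a baseline of 4, 2 points from 8 and 4 points from 16. Whether that threshold is right is for the sponsor.

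**2. Whether the early-termination battery can stand in for the scheduled tests.** Section 6.2 allows 10 days either side, weekends excluded, and 3.1 allows the 10 sessions to take 2 to 4 weeks. Assume treatment starts on the first working day of Week 1 with daily sessions, and a participant is withdrawn at session 3 and tested that day:

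- against the end of a 2-week course (working day 10): 10 - 3 = 7 working days early, inside the window;
- against the end of Week 4 (working day 20): 20 - 3 = 17 working days early, outside;
- against Week 8 (working day 40): 40 - 3 = 37 working days early, outside.

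So whether this one score could count as post-treatment depends on a target date that the plan does not define for an early stopper. It cannot count as follow-up under 6.2's own window. In every case there is one post-baseline score at most, where the plan calls for two.

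**3. Illustrative size.** Let f be the fraction of an arm lost and D the amount by which the mean change of those who stay exceeds that of those who leave. The mean of those who stay exceeds the mean of the whole arm by f x D. Assume 3 of 15 are lost from one arm and nobody from the other, so f = 3/15 = 0.20:

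- D = 0.25 SD: 0.20 x 0.25 = 0.05 SD
- D = 0.5 SD: 0.20 x 0.5 = 0.10 SD
- D = 1.0 SD: 0.20 x 1.0 = 0.20 SD

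One loss (f = 1/15) gives 0.03 to 0.07 SD and five (f = 5/15) give 0.17 to 0.33 SD, for D from 0.5 to 1.0 SD. With losses in both arms the net shift is the difference between the two products and may be near zero. For scale, with an assumed two-sided 5% level and 80% power, a two-sample comparison of change detects 1.06 SD at 15 versus 15 and 1.13 SD at 12 versus 15.

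**The case against.** The best defence is that the sections cover different cases. Section 6.2 is about windows and missed sessions, its retention sentence follows text on scheduling conflicts, and 6.1.2 sends withdrawals and drop-outs to 4.4.2 to 4.4.4. Section 4.4.3 speaks of withdrawing from the study and from all assessments, which suggests that the two can be separated. This is a coherent reading, but 6.2 does not limit itself in that way. Even if it did, the scheduled tests would not be restored: the withdrawn participant would then have only the conditional battery in 5.2.4.

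It can also be said that differential exit is not shown. The table in 11.3.3 reports similar rates for real and sham stimulation, with discomfort at 10.4% and 13.4%. That stands as a reason not to assume a direction. The same section notes hypomania in a few patients given tDCS, so imbalance remains plausible. Finally, Aim 2 is a pilot, and 0.10 SD is about a tenth of the difference it could detect (0.10/1.06). That bears on priority and does not remove the inconsistency.

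A reader might infer more than the documents support:

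- That any stop of stimulation is an exit. Continued discomfort ends only the session, and a moderate-severe rating gives a choice; someone who stays in falls under 6.2 without conflict.
- That symptom exits generally lose the Week 4 test. For the scored rules this does not follow, as shown above.
- That an early score would be analysed as the Week 8 result. Section 5.2.4 says which assessments are done, not which time point they represent. The post-treatment and follow-up batteries in 5.4 are the same, and 6.2 makes an out-of-window primary outcome a reportable deviation.

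**Conclusion.** The point holds in a limited form. Sections 5.2.3 and 4.4.2, read with 6.2, give two dispositions for a participant withdrawn early for side effects or symptoms. No text keeps that person on the scheduled span tests or says what time point the early-termination battery represents. In Aim 2 both post-baseline tests are at risk for side-effect exits, clinically observed mania and high suicide risk. For the scored symptom rules only follow-up is at risk, if the mid-point assessment means the end-of-Week-4 visit.

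The resulting bias cannot be sized from the documents. The 0.05 to 0.20 SD rests wholly on assumed figures (3 of 15 lost, all from one arm, change 0.25 to 1.0 SD worse) and should not be read as an estimate. The case for changing the text is that these losses are selective, each one is 1/15 = 6.7% of an arm, and the remedy is cheap.

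**What to change.** Reconcile 4.4.2, 4.4.3, 5.2.3, 5.2.4 and 6.2 by stating two things separately: what happens to stimulation and training, and what happens to outcome assessment. The clinical stopping rules stay with the sponsor. Specifically:

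1. State that participants who stop treatment for any reason are still invited to the post-treatment and follow-up MCCB span visits, if willing and able and unless they decline assessments under 4.4.3.
2. Define the target dates of those visits for early stoppers from randomisation, because the end of treatment is not a usable anchor for them.
3. Record the early-termination battery at its actual date. Do not treat it as a post-treatment or follow-up score unless it falls within the 6.2 window of that visit's target date.
4. Say which Aim 2 visit, if any, the mid-point assessment in 5.2.3 refers to.

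The cost is protocol wording, some effort to re-contact participants, and up to two visits for each of the few who stop. Those visits are already planned and paid for in 5.7 ($30 + $50 = $80 per participant). Some will decline, so the change reduces the loss of outcome data without removing it.
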